#### 1.4.2 Intervention Arm

In Part A: Participants randomized to the intervention arm will have a same-day visit with a study physician. Those who are interested in being treated for their HCV, and have no contraindication, will (a) have standard of care baseline laboratory testing drawn and be given a one-week ‘Starter-Pack’ (7 day supply) of sofosbuvir 400mg/velpatasvir 100mg. Subsequent supplies of DAA therapy will be distributed to HCV RNA test positive participants as one 21-day and one 56 day supply to complete a 12-week treatment course. Those participants with negative confirmatory HCV RNA testing will be contacted via telephone and instructed not to begin the medication, and will not be given additional medication supplies.

Participants will be contacted weekly while receiving sofosbuvir/velpatasvir by text message to assess adherence, potential adverse effects, and offered other tele-support as needed. Scheduled study visits will occur at 4 weeks, upon treatment completion or discontinuation (study week 12), study week 16 (corresponding to SVR4), study week 24 (corresponding to SVR12), study week 36, and study week 48. Each study visit will consist of laboratory testing, semi-structured interview, and physician visit. Additional medical visits may be scheduled at the participants’ request. Additionally, each participant will be scheduled for a one-time counseling session for prevention of reinfection during their course of treatment. Referral to harm reduction and/or opioid substitution treatment programs will be provided for interested participants, but utilization of these services is not a condition of enrollment in the study or of HCV treatment provision.

In Part B: Participants will be enrolled in the telemedicine arm, and will have a same-day or next-day telemedicine visit with the hepatitis C provider. Initial evaluation will be either via telephone, video, or in-person at the syringe service program depending on patient preference. Blood testing will be arranged at local community laboratory facilities. Participants with positive HCV RNA will have delivery of a 28 day supply of sofosbuvir/velpatasvir, and a 56 day supply after completion. Weekly check-ins will occur by phone, and participants will have clinical laboratory monitoring at week 4 (optional), week 12, every 12 weeks thereafter until completion of follow up. Participants will complete a short structured survey at weeks 0, 12, 24, 36, and 48, also over video or telephone.

#### 1.4.3 Usual Care Arm

During Part A: Participants randomized to the usual care arm will have a same-day lab draw for confirmatory HCV RNA testing. Those who test RNA positive will be referred to local clinic or community based HCV medical providers.

Participants will be contacted monthly via telephone for a short questionnaire. Scheduled study visits will occur at study weeks 12, 24, 36 and 48 for semi-structured interviews and HCV RNA testing.

During Part B: no participants will be assigned to the usual care arm

#### 1.5 Hypothesis

We hypothesize that the ST&RT intervention will be accepted by HCV infected PWID aged 18-29, and lead to higher rates of treatment initiation, completion and SVR12 compared to the usual practice of referral to community HCV providers.

#### 1.6 Primary Outcome

[figure not shown]
The proportion of participants who achieve sustained virologic response defined as an undetectable HCV RNA viral load 12 weeks after the cessation of treatment (SVR12), in the intervention arm compared to the usual care arm by study week 48.

#### 1.7 Secondary Outcomes

[figure not shown]
1. The proportion of participants who initiate treatment for HCV in the intervention arm compared to the usual care arm by study week 48.
2. The proportion of participants who complete the prescribed course of treatment for HCV in the intervention arm compared to the usual care arm by study week 48.3. The proportion of participants after initiating HCV treatment did not complete it compared to the usual care arm by study week 48.
4. The proportion of participants in both arms who achieve SVR 12, or are RNA negative at baseline, that have HCV reinfection (defined in section 5.5) by study week 48.
5. To characterize the HCV genotype and presence of resistance associated substitutions (RAS) in those treated patients with HCV reinfection or relapse.
6. To examine impact of engagement in HCV treatment on substance use behaviors and injection risk.
7. Qualitative assessment using semi-structured interviews to evaluate the acceptability of the intervention versus usual care, the barriers to initiate and complete treatment, and factors influencing successful treatment outcomes
8. To assess the feasibility, safety, and effectiveness of a tele-medicine based rapid start intervention for hepatitis C treatment in young people who inject drugs.

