### 1.4 Study procedures

#### 1.4.1 Enrollment and sampling

Potential research participants will be recruited by referral from an ongoing NIH funded study aiming at preventing HCV among young current injectors (R01DA041501), hereafter referred to as the parent

study. The parent study will conduct a randomized, controlled trial to assess the effectiveness of a “Staying Safe” prevention intervention in reducing injection-related risk behavior and HCV incidence among 18-29 year-olds who inject opioids (heroin and/or POs) and test HCV and HIV antibody-negative at screening. The parent study is continuing to enroll participants and perform HCV testing. Whereas previous procedures would have required that the participant be referred physically to the syringe service program, we are now allowing for remote enrollment by phone or video as the first point of contact. Since the parent study is still operating, we expect to continue to receive referrals of HCV-infected people. Candidates for the parent study who test HCV antibody positive at the screening visit, will be immediately offered enrollment in ST&RT. The target sample size of 27 participants per arm is selected to show a hypothesized difference in SVR12 rates of about 35% with 80% power at a level of 0.05. Participants who are enrolled but negative on confirmatory testing (an expected 25% of participants) will be replaced. These participants will not receive treatment interventions but continue to be followed for monitoring of HCV re-infection incidence. We anticipate enrolling 36 participants per arm to achieve the target of 27 confirmed infections per arm.

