Participants in the control arm will be provided facilitated referral to community HCV providers by an on-site care coordinator already facilitating care at the community site. HCV RNA negative participants will be called to inform them of these results, and then discontinued from the study. HCV RNA positive participants will be asked during the semi-structured interviews as at 12, 24, 36 and 48 week if they engaged in HCV treatment to assess whether their HCV referral has been filled, and to record their current HCV treatment status. They will also receive repeat HCV RNA testing at week 12, 24, and 48. Participants that have started treatment will be asked to sign consent for release of medical records pertaining to HCV-related laboratory testing to determine achievement of treatment response.

During part B, HCV RNA positive participants will have a 28-day supply of medications delivered, or available for pickup, as they prefer. The schedule of visits will be similar except that laboratory testing at week 4 will be optional, and all visits will be offered through telemedicine.

The three arms will be compared for the main outcome of SVR12 using a modified intention to treat analysis in which participants will be analyzed in the group they are randomized except for those who are (a) discontinued due to HCV RNA negative status or (b) found to have previously undiagnosed HIV at enrollment. Secondary outcomes will be compared using the same modified intention to treat design.

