## 5.5 Monitoring for reinfection

Participants in the intervention arm who receive treatment will have two post-treatment HCV RNA PCR tests, at 24 and 48 weeks, to monitor for re-infection after treatment completion. Participants who did

not receive treatment, either because of HCV-negative status or because of other reasons, will have HCV RNA PCR testing at 24 and 48 weeks. All participants in the control arm, regardless of HCV RNA status, will have HCV RNA PCR testing at 24 and 48 weeks, but it is expected that these may not be “post-treatment,” as we expect treatment initiation to be delayed for the control participants.

True reinfection will be defined as a positive HCV RNA PCR with a different HCV genotype, occurring anytime after a documented SVR 12 (negative HCV RNA PCR 12 weeks or more after treatment completion).

Participants who (1) did not have a documented SVR 12 but did have a documented end-of-treatment response or SVR 4, and subsequently have a positive HCV RNA PCR OR (2) have a positive HCV RNA PCR after documented SVR12 with the same genotype as the initial infection, will be classified as possible reinfections. These participants will then be reclassified as either true reinfections or relapses based on viral sequencing of their baseline HCV infection compared to subsequent positive HCV RNA PCRs.

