### 5.6 Monitoring for incident HCV infection

Participants who had a negative HCV RNA PCR at baseline (or whose HCV RNA PCR became negative without treatment), who subsequently have a positive HCV RNA PCR will be considered incident HCV infections, but not reinfections.

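### Secondary outcome 4 counts baseline RNA-negatives who in practice cannot have the reinfection event, the sections disagree on following and analysing them, and the proportion test ignores unequal time at risk (minor)

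*Combined protocol and SAP*

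**What the plan says.** **Population.** Section 1.7 item 4 sets its denominator and event as follows: "who achieve SVR 12, or are RNA negative at baseline, that have HCV reinfection (defined in section 5.5) by study week 48". The item covers both arms, which I read as the two randomized Part A arms; section 0.2 item 6 says reinfection is not analysed for the telemedicine cohort.

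**Event.** Under 5.5 a true reinfection is a positive RNA test with a different genotype, "occurring anytime after a documented SVR 12 (negative HCV RNA PCR 12 weeks or more after treatment completion". A possible reinfection, later resolved by sequencing, is either a same-genotype positive after SVR12 or a positive in someone who "did not have a documented SVR 12 but did have a documented end-of-treatment response or SVR 4". For participants RNA-negative at baseline who later turn positive, 5.6 says they "will be considered incident HCV infections, but not reinfections".

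**Follow-up of RNA-negatives.** Section 1.4.1 says, without naming an arm: "These participants will not receive treatment interventions but continue to be followed for monitoring of HCV re-infection incidence". Section 3.0 keeps intervention RNA-negatives in 12-weekly research visits. Its control-arm paragraph says: "HCV RNA negative participants will be called to inform them of these results, and then discontinued from the study". Section 5.5 has every control tested at weeks 24 and 48 whatever the RNA status.

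**Analysis set.** The modified intention-to-treat rule in 3.0 removes those "discontinued due to HCV RNA negative status", and adds: "Secondary outcomes will be compared using the same modified intention to treat design". Section 8.3.1 excludes participants with a negative confirmatory RNA test, with no distinction by arm, in its primary-analysis paragraph.

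**Test.** Section 8.3.1 compares reinfection proportions by chi-square or Fisher's exact test. Section 5.5 expects treatment to start later in control.

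**The concern.** A proportion can be interpreted only if everyone in the denominator can have the event and is watched for a comparable time. Item 4 fails on the first count by its own cross-reference to 5.5. The other sections leave it open whether the RNA-negatives are in the denominator, and whether that is so in both arms. The test in 8.3.1 fails on the second count, because a participant cured later has less of the 48 weeks left in which a reinfection could be seen.

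Section 2.2.4 names reinfection after cure as a concern in this population. An excess or deficit produced by the denominator or by the calendar could be read as a consequence of rapid treatment.

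**Working it through.** **Inputs.** From 8.1: 27 RNA-positive participants per arm, 75% of enrollees viremic, SVR12 in 11/27 control and 78% intervention. From 1.4.2: intervention SVR12 at week 24 and end of treatment at week 12. The documents give no control delay and no reinfection rate; both are assumed and ranged below.

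**The plan's own figure.** 27 / 0.75 = 36 enrolled per arm, as stated. RNA-negatives: 36 − 27 = 9 per arm. Intervention cures: 0.78 × 27 = 21.

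**1. Denominator alone.** Let the reinfection risk among the cured be the same value p in both arms, with events only among the cured.

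| Handling of RNA-negatives | Intervention | Control | Ratio |
|---|---|---|---|
| Kept in both arms (item 4) | 21p/30 | 11p/20 | 0.70/0.55 = 1.27 |
| Dropped in both (8.3.1 exclusion carried over) | 21p/21 | 11p/11 | 1.00 |
| Dropped in control only (3.0 read literally) | 21p/30 | 11p/11 | 0.70 |

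Under item 4, 9/30 = 30% of the intervention denominator and 9/20 = 45% of the control denominator cannot contribute an event. With 23 intervention cures (85%), the first and third ratios become (23/32)/(11/20) = 1.31 and 23/32 = 0.72.

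**2. Time at risk alone, cured participants only.** Risk = 1 − exp(−rate × weeks/52), same rate in both arms. From SVR12, the intervention arm has 48 − 24 = 24 weeks and control has 24 − delay. From end of treatment, which 5.5 also allows through its possible-reinfection route, the figures are 48 − 12 = 36 and 36 − delay. At an assumed 10 per 100 person-years:

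| Control delay (weeks) | Ratio from SVR12 | Ratio from end of treatment |
|---|---|---|
| 4 | 1.20 | 1.12 |
| 8 | 1.49 | 1.28 |
| 12 | 4.51% / 2.28% = 1.98 | 6.69% / 4.51% = 1.48 |
| 20 | 5.89 | 2.21 |

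The SVR12 ratios barely move with the rate: from 5 to 30 per 100 person-years, the 12-week value runs from 1.99 to 1.93. At a 24-week delay no control time remains after SVR12. The SVR12 column assumes that each SVR12 is documented on its due date.

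The two distortions multiply. At a 12-week delay from SVR12, keeping RNA-negatives in both arms gives 1.27 × 1.98 = 2.5, and dropping them in control only gives 0.70 × 1.98 = 1.4.

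**3. Expected events.** At 10 per 100 person-years and a 12-week delay, counted from SVR12: 21 × 0.0451 = 0.95 in intervention and 11 × 0.0228 = 0.25 in control, about one event in all.

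**4. Effect on the test.** With 21 and 11 cured and no control events, Fisher's test needs 8/21 v 0/11 for p < 0.05. Summing the binomial probabilities under equal rates and a 12-week delay, it is significant with probability about 0.0007 at 10 and 0.004 at 30 per 100 person-years.

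**The case against.** **The exclusion may already cover both arms.** Section 8.3.1 excludes RNA-negatives without regard to arm, and 3.0 carries the modified intention-to-treat set to secondary outcomes. Together these point to the 1.00 row. A reader might infer from 3.0 that the plan drops RNA-negatives in control only; the documents do not establish that. It needs the word discontinued taken literally in the modified intention-to-treat rule and 8.3.1 set aside. The both-arm reading does not rescue item 4, however, because it contradicts item 4's stated population.

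**The plan already separates the two events.** Section 5.6 does so, and the descriptive list in 8.3.1 names reinfection and incident infection separately. This stands: the mismatch is largely one clause in 1.7, which makes it cheap to correct.

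**Evidence on control follow-up is uneven.** Sections 1.4.1 and 5.5 are the clear statements against discontinuation, and only 5.5 names the control arm. Sections 2.2.3 and 5.2.1 and the 5.1 schedule are consistent with continued testing but do not settle it.

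**The time-at-risk ratios depend on the clock.** This stands. A reader might take a doubling, or nearly sixfold at 20 weeks, as the size of the problem. Those values hold only from an SVR12 documented on time. From end of treatment they are 1.5 and 2.2.

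**Formal inference is hardly affected.** This also stands. A reader might infer that the plan risks a false significant result; step 4 shows that Fisher's test would almost never give one.

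**Conclusion.** The point holds as a minor one. Item 4 is wrong as written: its denominator includes people whom 5.5 and 5.6 between them keep out of the event. The sections on follow-up and analysis set cannot all be followed, and the choice among them moves the apparent ratio between 0.70 and 1.27 when reinfection among the cured is equal. The literal control-only reading at 0.70 is the least supported. Unequal time at risk is a separate distortion: about 2.0 from SVR12 or 1.5 from end of treatment, for an assumed 12-week delay and identical rates.

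These figures rest on planned counts, which Part A will not reach because its analysis is limited to enrollment through March 1, 2020. What is at stake is a misread descriptive contrast on about one expected event. The formal test result is essentially unaffected, and so is the primary outcome.

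**What to change.** (a) Amend 1.7 item 4 to reinfection among participants with documented SVR12. Report incident infection among baseline RNA-negatives as a separate outcome, in line with 5.6 and the descriptive list in 8.3.1.

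(b) Reconcile the control-arm discontinuation sentence in 3.0 with 1.4.1, the intervention-arm text in 3.0, and 5.5, so that RNA-negatives are handled alike in both arms. State that the RNA-negative exclusion does not apply to the incident-infection outcome. If control RNA-negatives have already been discontinued, make no between-arm comparison in that group.

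(c) In 8.3.1, replace the reinfection proportion test with a descriptive report by arm: events and person-time from documented SVR12, with exact Poisson intervals. Label it descriptive, since it conditions on cure. List sequencing-confirmed reinfections before SVR12 separately, and say openly that 5.5 counts them but this rate does not.

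**Cost.** The change is wording in 1.7, 3.0 and 8.3.1. The intervals will be wide. At planned size and a 12-week delay, full follow-up gives 21 × 24/52 = 9.7 person-years against 11 × 12/52 = 2.5. One intervention event would be 10.3 per 100 person-years (95% CI 0.3 to 57.5), and no control events would leave an upper limit of about 145. Control study tests fall only at scheduled visits (weeks 12, 24, 36 and 48 in 1.4.3), so some control SVR12 dates will depend on consent to release outside records.

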## 1.8 Schematic

### 1.8.1: Part A Schematic

## 1.8.2: Part B Schematic

## 2.0 Introduction

### 2.1 Background

Our proposed pilot study will examine the effectiveness and acceptability of a novel rapid) treatment initiation strategy that if found effective could be further studied as part of a new model for HCV treatment delivery in young PWID, namely: Seek, Test and Rapid Treat (HCV ST&RT, a modification of the well-known Seek, Test and Treat model for HIV). This strategy has potential to avoid the attrition observed on the HCV care cascade and reach the population most important for treatment as prevention, young PWID. This study focuses on Rapid Treatment initiation and will not study the Seek and Test components, however we will refer to the strategy as HCV ST&RT throughout this proposal for simplicity.

The United States has been experiencing a dramatic opioid epidemic among young people for over a decade. Between 2002 and 2013, heroin use in the United States has increased by 63%, with the largest increase (109%) in individuals aged 18-25. The rise in injection drug use has been accompanied by increases in incident HCV infection. Cases of acute HCV increased more than 2.5-fold from 2010-2014 with the greatest increases among people age 20-29. Recent HCV outbreaks across several states reflect the widespread transmission of HCV in PWID, and modeling studies indicate that counties with higher rates of drug overdose deaths and prescription opioid sales are vulnerable to HCV outbreaks in the future.

The recent development of direct acting antivirals (DAAs) with high efficacy and tolerability has revolutionized treatment of HCV. Despite this, PWID are faced with multiple barriers to successful treatment: in addition to the effects of substance use and its comorbid conditions, PWID face mistrust within the medical system, explicit sobriety requirements from insurers, and a lengthy prior authorization process which necessitates extensive medical workup before initiating treatment. Indeed, data from New York City suggest that only 38% of HCV-diagnosed PWID are engaged in care, and only 12% have initiated treatment. Engaging and treating HCV in young PWID is further complicated by the common reluctance of this population to prioritize an infection that is unlikely to affect them for more than a decade.

Overcoming the barriers to treat young PWID is essential: DAA therapy has the potential to impact the HCV epidemic, and among young PWID, it has the potential to prevent incidence, reduce prevalence, and potentially eradicate HCV infections entirely. However, modelling studies on HCV prevalence show that in order to achieve elimination of HCV, extensive treatment scale-up is needed among PWID, the group at highest risk of transmitting disease. The concept of treatment-as-prevention to control communicable disease is a cornerstone of public health for a number of diseases, including tuberculosis, sexually transmitted infections, and most recently HIV. In fact, the demonstration of this concept helped to change the paradigm of HIV treatment, supporting early initiation of treatment before CD4 count reductions.

Rapid initiation of therapy in individuals at high risk of transmitting disease can help to minimize transmission. In a San Francisco study of HIV, the same-day initiation of antiretroviral therapy led to significantly faster time to viral suppression without sacrificing effectiveness. This outcome was accomplished using an intervention consisting of (a) same-day access to an HIV provider, (b) accelerated insurance approval process (c) pre-approved regimens (d) 5-day starter packs, (e) observed administration of first dose, and (f) telephone follow-up. A similar model is now being implemented in sexually transmitted infection clinics in New York City (JUMPSTART program). In contrast to HIV where

there is an added challenge of retaining patients in care, the curable nature of HCV would appear to make it even more amenable to a Rapid Treatment Strategy.

In the past, a rapid treatment initiation approach would not have been possible for HCV. Interferon based therapies came with high toxicity, the need for supervised injection, and extensive medical monitoring. The advent of DAAs have allowed for increased decentralization of HCV management and treatment: tele-consultation with specialists is allowing treatment prescriptions by primary care physicians, and the ease of DAA therapy can facilitate treatment to be located at community sites rather than in specialty clinics. Our group, among others, has demonstrated the safety and effectiveness of medical evaluation and treatment with DAAs located at a syringe services program (SSP) in New York City, with sustained virologic response at 12 weeks (SVR12) of 85%, and low rates of re-infection [unpublished data]. We are now studying this model on a larger scale in a randomized control trial comparing accessible SSP-based care with standard of care (R01 DA041298). However, our experience suggests that accessible care may not be sufficient incentive for young PWID to seek HCV treatment. This is especially true for suburban, housed, young PWID who are less likely to frequent existing harm reduction services than their older counterparts. To truly impact the prevalence and incidence of HCV, models of HCV treatment delivery and prevention need to focus on young, active PWID (where ongoing transmission is most concentrated).

Evidence suggests that high rates of HCV treatment engagement of young PWID is not possible without aggressively addressing the various barriers complicating the treatment cascade, specifically the delay between HCV confirmation and treatment initiation that currently results not only from the need for linkage to an HCV provider but also from (a) extensive pre-treatment lab testing (genotype, fibrosis assessment, and resistant testing) and (b) lengthy insurance prior authorization process.

Our proposed pilot study will examine the acceptability of HCV Seek, Test and Rapid Treatment (HCV ST&RT) and the effectiveness of Rapid Treatment Initiation in young PWID involving (1) immediate initiation of DAA treatment at time of diagnosis using starter packs, (2) community based treatment location, and (3) minimal in-person monitoring with text message-based support during the treatment process. We will achieve this using DAA treatment with a pan-genotypic treatment regimen, leveraging our existing community partnerships with local SSPs, and using mobile health technology to communicate with participants without necessitating frequent office visits.

